Collecting/reporting of adverse events: In the study, all adverse experiences, whether expected or unexpected, were reported to the DSMC. Any adverse experience occurring to a greater severity than expected was reported to the Washington University Human Research Protection Office (HRPO) and the Pediatric Clinical Research Unit (PCRUC)/Clinical Research Unit (CRUC)/Clinical Trials Unit (CTUC), and to the National Institutes of Health (NIH). The HRPO, PCRUC/CRUC/CTUC, the PCRUC Research Participant Advocate (RPA) and NIH will be notified of any serious unexpected adverse experience within seven working days of occurrence. If the event is fatal, the HRPO, PCRUC/CRUC/CTUC, RPA and NIH will be notified within 24 hours of occurrence. The HRPO, PCRUC/CRUC/CTUC, and NIH received annual reports regarding all adverse experiences.

Data and Safety Monitoring Plan: The Data and Safety Monitoring Plan (DSMP) for this protocol will include adverse event and other reporting by the P.I. to IRB and oversight and monitoring by the P.I. as well as the CRUC/PCRUC Research Participant Advocate (RPA). Summary reports to the IRB will be provided annually. Serious adverse events will be reported to the IRB, to the CRUC/PCRUC Advisory Committee via the RPA, and to the Sponsor: (a) death – immediately; (b) life-threatening—within 7 calendar days; and (c) all other SAEs within 7 calendar days using the Electronic SAE System.

The stopping criteria and guidelines included the following: 1) if, based on a totality of evidence likely to influence clinical practice, there was clear evidence of harm or harmful side effects of the procedures used in this protocol then the protocol would be suspended at least until acceptable modifications have been made; 2) in the event that a SAE occurred that was judged to increase risk to all participants, the study would be stopped and an investigation would be conducted and a findings report generated and provided to the Sponsor, IRB and the CRU/PCRU Advisory Committee via the CRU/PCRU RPA before the study were to be resumed; 3) were there SAEs or AEs that occurred at a frequency greater than 5%, they were added to the consent document if not already addressed, and enrollment would be halted while a determination was made regarding the potential risks to participants. All reports sent to IRB were reported to the Sponsor (NIH), per HRPO guidelines. Thus, the DSMP for this protocol was in full compliance with the Washington University PRU/CPCRU/CTU DSMP.

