This project will utilize sensitive, early biomarkers of disease risk, including whole-body adiposity, hepatic triglyceride content and carotid IMT, directly relevant to diabetes and cardiovascular disease risk, respectively. **The overall aim of this two-study research plan is to characterize risk using these sensitive biomarkers in children with mental health disorders, and evaluate the magnitude of change observed in these biomarkers in children receiving an established weekly behavioral weight-loss (BWL) intervention.** This will be accomplished with a randomized, controlled test of the effects of a 16-week behavioral weight loss intervention on CTGC, PDFF and IMT in overweight/obese antipsychotic (AP)-treated children randomized 2:1 to weekly BWL treatment or monthly diet and exercise education or usual care (UC), versus nonpsychiatric (NP) overweight or obese children undergoing the weekly BWL treatment.

Study Aims for this pilot randomized controlled trial:

Aim 1: To evaluate the main effect of time of 16 weeks of a BWL intervention on DEXA-measured whole body adiposity in overweight/obese antipsychotic (AP)-treated children compared to nonpsychiatric (NP) overweight or obese healthy controls, and in AP-treated youth randomized to monthly Usual Care (UC).

Aim 2: To evaluate the main effect of time of 16 weeks of a BWL intervention on PDFF in overweight/obese AP-treated children compared to NP overweight or obese healthy controls, and in AP-treated youth randomized monthly UC.

Aim 3: To evaluate the main effect of time of 16 weeks of a weekly behavioral weight loss intervention on CIMT in overweight/obese AP-treated children compared to NP overweight or obese healthy controls, and in AP-treated youth randomized monthly UC.

Primary Hypothesis: *Change in DEXA-measured total fat and PDFF/IMT will be more pronounced in the weekly weight loss intervention groups compared to the monthly Usual Care intervention.*

Exploratory Aims:

a) To evaluate the effects of 16 weeks' of weekly versus monthly weight loss intervention on changes in standard cardiometabolic risk factors (e.g., fasting lipids, insulin, glucose, adiponectin, fibrinogen, high sensitivity C-reactive protein and very low density lipoprotein particle size).

b) To evaluate baseline psychiatric symptom severity on treatment adherence and changes in biomarkers during treatment.

PARTICIPANT RECRUITMENT & SELECTION

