Hepatic ¹H Magnetic Resonance Spectroscopy (MRS)-estimated proton density fat fraction (PDFF): 1.5T Siemens Magnetom Vision scanner (Siemens, Erlanger, Germany) were conducted to quantify hepatic triglyceride content.²⁴ Participants were placed in a supine position the scanner using standard array coils. Hepatic triglyceride content was determined within a voxel size of 15 × 15 × 20 mm³ by using a point resolved spectroscopy (PRESS) single-voxel technique. Data were averaged from 20 scans and obtained with a repetition time of 2 seconds. Spectra were acquired at echo times of 24, 30, 35, 40, 50 ms at upper left lobe and mid to lower lobe voxels and at an echo time of 24 ms at the mid-lobe voxel to estimate and correct for the T2 decay of the signals. Images were corrected for relaxation and analyzed using jMRUI, a Java-based graphical user interface quantification package that allows time-domain analysis of *in vivo* MR data.²⁵ All frequencies, i.e., chemical shifts, were measured relative to the principal water ¹H resonance, which is referenced as zero Hz.

Dual Energy X-ray Absorptiometry (DEXA): to assess Percent total body fat and percent total fat-free mass (Hologic QDR 1000/w, Waltham, MA).²⁶ Appendicular skeletal muscle mass will be estimated from these data as described and validated by Heymsfield et al.²⁷ In addition, changes in bone mineral density (BMD) will be calculated for the exploratory aim. The error of regional fat free mass determination by this technique, as compared with computerized tomography, is less than 5%.^{26,27}

9-13-MHZ B-mode Carotid Ultrasound: (Vivid E9, GE Medical Systems using automatic edge detection software) for the measurement of carotid intima media thickness (IMT) in the longitudinal and cross-sectional axes. IMT was expressed as the average minimum, mean and maximum thickness measured over a 1 cm region of the bilateral posterior common carotid walls approximately 1-2 cm proximal to the carotid bulb. Studies will be reviewed and analyzed by two independent readers, who will be blinded to subject data. The intra- and inter-observer intraclass correlation coefficients for IMT measurements at our laboratory are 0.91 and 0.88, respectively.²⁸

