Previously published carotid IMT numbers indicating significant differences between obese children with and without metabolic syndrome criteria provide a crude proxy for the difference between an active intervention group and UC, suggesting that we should be able to detect a difference of 1.27 +/- 0.005 in intima media stiffness (units are logarithmically transformed and are therefore unitless).¹⁰ Power to detect differences in CIMT between the 3 treatment groups using a sample size of 20 per group, an alpha of 0.05, and an effect size of 0.16 was calculated to be 0.17.

Previous reports of hepatic triglyceride content in the general population indicate that 33.6% of the population meet criteria for hepatic steatosis (> 95th percentile of hepatic triglyceride content of 5.56%, corresponding to 55.6 mg/g) based on weight criteria, with obese patients being more likely to meet criteria for steatosis than healthy controls.³⁵ Power to detect differences in Hepatic Triglyceride Content between the 3 treatment groups using a sample size of 20 per group, an alpha of 0.05, and an effect size of 0.49 was calculated to be 0.92.

DEXA power calculations were based on previously noted weight loss of up to 8-10% in other studies of behavioral weight loss interventions between 2 and 5 months in length with known SDs on the observed mean change.^{36,37} Based on our previous experience with antipsychotic treated and untreated children, we anticipated that the baseline DEXA % fat would be 14-15 kg of body fat, or roughly 30-40% body fat. Anticipating up to a 5% loss from baseline fat measured by DEXA, less than the 8-10% observed in other studies, due to potential effects of the ongoing mental health condition and the antipsychotic treatment in this sample, we estimated a difference between active treatment groups (AP-treated vs. NP) of 2 +/-3 kg loss from a baseline of 15 kg total fat. Power to detect differences in DEXA Total Fat between the 3 treatment groups using a sample size of 20 per group, an alpha of 0.05, and an effect size of 0.53 was calculated to be 0.96.

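### The power text says a CIMT difference should be detectable, but it cites a stiffness figure rather than the measured thickness and then reports power of 0.17

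*Combined protocol and SAP*

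**What the plan says.** All references are to Appendix I (Protocol Synopsis) unless stated.

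- **Power, CIMT paragraph.** Published carotid figures comparing obese children with and without metabolic syndrome are said to "provide a crude proxy for the difference between an active intervention group and UC". From this the text concludes that "we should be able to detect a difference of 1.27 +/- 0.005 in intima media stiffness", adding that "units are logarithmically transformed and are therefore unitless".
- **Same paragraph, next sentence.** Power for the three-group CIMT comparison is given for 20 per group: "an alpha of 0.05, and an effect size of 0.16 was calculated to be 0.17". The type of effect size is not named, and no step leads from the stiffness figure to 0.16.
- **Carotid Ultrasound (assessments section).** The instrument is used "for the measurement of carotid intima media thickness (IMT) in the longitudinal and cross-sectional axes". Results are expressed as minimum, mean and maximum thickness. No stiffness index is defined.
- **Appendix II, Table 1.** Baseline CIMT is reported in cm: 0.0484 (SD 0.0070) for the combined sample.
- **Specific Aims.** CIMT is the outcome of Aim 3, and IMT is named in the Primary Hypothesis, where change "will be more pronounced in the weekly weight loss intervention groups compared to the monthly Usual Care intervention". It is not in the separate list of exploratory aims.
- **Analytic approach.** CIMT is one of three risk factors in the primary goal. It is analysed by ANCOVA on the 16-week value, with baseline and a three-level group factor.

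**The concern.** Two adjacent sentences disagree. The first tells the reader that the trial can detect a CIMT difference. The second says that the chance of doing so, at the effect size the plan itself uses, is about one in six. The first sentence also concerns a different quantity on a different scale, so the plan states no target difference for the CIMT outcome in the units in which it is measured. Since 0.16 has no stated origin, a reader cannot judge whether it is a plausible effect.

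This matters because CIMT belongs to the primary goal. A reader who relies on the detectability sentence could take a non-significant CIMT contrast as evidence that the intervention does not affect the carotid wall. At an effect size of 0.16 the three-group test would miss a true effect about 83% of the time (1 − 0.17).

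**Working it through.** **Inputs.** From the Power section: 3 groups, 20 per group (N = 60), alpha 0.05, effect size 0.16. From Table 1: CIMT mean 0.0484 cm, SD 0.0070 cm. From Specific Aims: 2:1 allocation of antipsychotic-treated children to weekly treatment or UC. The baseline-to-week-16 correlation r is not given, so a range is assumed.

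**1. Reproduce the plan's figure.** Read 0.16 as Cohen's f in a one-way F test with 2 and 57 df. The noncentrality is f² × N = 0.16² × 60 = 1.536, and power from the noncentral F distribution is **0.174** (stated 0.17). The same formula gives 0.922 at f = 0.49 (hepatic triglyceride, stated 0.92) and 0.956 at f = 0.53 (DEXA total fat, stated 0.96), which supports this reading. Reading 0.16 as a two-group standardized difference gives 0.073 (normal approximation, two-sided), which does not match.

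**2. Check the scale.** Taken as cm, 1.27 would be 1.27 / 0.0484 ≈ 26 times the baseline mean and 1.27 / 0.0070 ≈ 181 times the SD. It cannot be a thickness difference.

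**3. Sample size that f = 0.16 would need.** For 80% power, 127 per group (381 in total), against 20 planned.

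**4. Allow for the planned ANCOVA.** If 0.16 is on the unadjusted scale, adjustment changes it to 0.16 / √(1 − r²), with one further error df used:

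| Assumed r | Adjusted f | Power |
|---|---|---|
| 0.5 | 0.185 | 0.22 |
| 0.7 | 0.224 | 0.31 |
| 0.8 | 0.267 | 0.42 |
| 0.9 | 0.367 | 0.70 |

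All are below 0.80.

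**5. Detectable difference in cm.** With 20 per group, 80% power needs f = 0.411. If UC alone differs from two equal groups, the gap in SD units is d = 3f / √2 = 3 × 0.4115 / 1.414 = 0.873. With SD 0.0070 cm:

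- unadjusted: 0.873 × 0.0070 = **0.0061 cm**, or 0.0061 / 0.0484 = 12.6% of the baseline mean;
- adjusted, multiplying by √(1 − r²): **0.0053, 0.0044 and 0.0027 cm** at r = 0.5, 0.7 and 0.9.

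On the same unadjusted basis, f = 0.16 corresponds to 0.339 × 0.0070 = 0.0024 cm.

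**6. Smaller UC group.** Groups of 20/10/20 illustrate 2:1 allocation. Keeping the 0.339 SD gap in UC, power falls to 0.12, and the unadjusted 80%-power difference rises to 1.133 × 0.0070 = 0.0079 cm.

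**The case against.** The plan is open about its limits. It describes a pilot, says that scarce prior research made power hard to calculate, calls its source a crude proxy and prints the low power. The 0.17 is correct arithmetic. All of this stands, and it makes the fault one of inconsistency and traceability, not miscalculation. Disclosure does not reconcile the two sentences, however, and the Primary Hypothesis carries no caveat.

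Several stronger readings are tempting, but the documents do not support them:

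- **That the power was calculated from the stiffness figure.** The origin of 0.16 is not stated. What can be shown is a missing derivation.
- **That 1.27 / 0.005 = 254 exposes an absurd standardized effect.** This assumes that the figure after +/- is the SD of the difference. The text does not say whether it is an SD, a standard error or something else.
- **That Aim 3 cannot be tested.** Aim 3 is worded as a main effect of time, for which no power is given. The 0.17 concerns the three-group comparison, so it bears on the Primary Hypothesis and the ANCOVA contrasts. The test can still be run; it lacks adequate power.
- **That 0.0024 cm is lost in reader error.** The inter-observer ICC of 0.88 gives 0.0070 × √0.12 = 0.0024 cm, but that is the error of a single reading. It is not comparable with a difference between group means, and the plan uses two readers and both carotids.

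It is also fair to say that 0.0061 cm, quoted alone, would overstate the detectable difference for a baseline-adjusted analysis. The adjusted range should accompany it.

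**Conclusion.** The point holds as a contradiction between adjacent sentences and a mismatch between the planning quantity and the outcome. The claimed detectability concerns stiffness, which the plan does not measure, and the plan's own power for the between-group CIMT comparison is 0.17. Adjustment for baseline would raise this to between 0.22 and 0.70 for assumed r from 0.5 to 0.9, still short of 0.80.

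The cm figures rest on 20 per group, UC alone differing, the combined baseline SD of 0.0070 cm standing in for the residual SD before adjustment, and an r that the documents do not supply. A UC group smaller than 20 makes every detectable difference larger. A reader might infer that the CIMT result is worthless or that IMT must leave the Primary Hypothesis. Neither follows: an adjusted estimate with its interval is useful in a pilot.

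**What to change.** 1. Delete the sentence claiming that a stiffness difference should be detectable, and show where 0.16 comes from or say that it is an assumption.
2. State that the between-group CIMT comparison is not adequately powered, with power of 0.17 at f = 0.16 and 20 per group.
3. Give the 80%-power detectable difference in cm with its assumptions: about 0.0061 cm unadjusted, and 0.0053, 0.0044 and 0.0027 cm at r = 0.5, 0.7 and 0.9 (20 per group, UC alone differing, SD 0.0070), larger if UC has fewer than 20.
4. Report the CIMT contrasts from the planned ANCOVA as baseline-adjusted differences with 95% confidence intervals, and say that a non-significant result will not be read as no effect.
5. Keep IMT in the Primary Hypothesis with this caveat. The document already reports 16-week results (Appendix II, Table 2), so any reclassification of IMT should be disclosed as post hoc.

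**Cost.** Text changes, plus confidence intervals from a model already planned. The stated prospects for CIMT become less favourable.

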Analytic approach: the primary goal was to compare changes over time in the three risk factors (CIMT/DEXA/PDDF) among three groups: obese AP-treated children randomized to the weekly intervention, obese NP children also receiving weekly behavioral weight loss treatment, and an obese usual care (UC) reference group. Comparisons of interest were between each of the two active treatment groups and UC, as well as between the two active intervention groups themselves (AP-treated vs. NP). Because this is a pre-post design with data collected only at baseline and at 16 weeks, our analytic strategy used an analysis of covariance (ANCOVA), in which the 16-week value of the risk factor is the dependent variable and the predictors are the baseline value of the risk factor and the study group (three level factor), with contrasts of interest listed above. Other analyses performed adjusted for covariates such gender and age to determine whether baseline-adjusted between group differences at 16 weeks can be explained by such covariates. Because of the relatively small sample size in this study, we performed separate analyses of covariance that include precisely one additional covariate, in addition to the baseline value of the risk factor of interest in each analysis.

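### The PDFF power of 0.92 is correct for Cohen's f = 0.49 with 20 per group, but neither that effect size nor the equal group sizes are supported

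*Combined protocol and SAP*

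**What the plan says.** In Appendix I, under Data Management, Safety & Adverse Event Reporting, the Power text introduces the liver-fat outcome with one published finding: "Previous reports of hepatic triglyceride content in the general population indicate that 33.6% of the population meet criteria for hepatic steatosis". The cut-off is described as the "95th percentile of hepatic triglyceride content of 5.56%, corresponding to 55.6 mg/g", and the only comparison added is one of direction, "obese patients being more likely to meet criteria for steatosis than healthy controls". The text then states the result: "Power to detect differences in Hepatic Triglyceride Content between the 3 treatment groups using a sample size of 20 per group", with "an alpha of 0.05, and an effect size of 0.49 was calculated to be 0.92". It does not name the effect-size index. It gives no PDFF mean, SD, expected change, group difference or baseline-to-week-16 correlation. The DEXA paragraph beside it does give a difference and an SD (2 ± 3 kg).

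Under Analytic approach, "our analytic strategy used an analysis of covariance (ANCOVA), in which the 16-week value of the risk factor is the dependent variable", with the baseline value and the three-level group as predictors. The Specific Aims randomise the antipsychotic-treated (AP) children 2:1 to weekly treatment or usual care (UC). The nonpsychiatric (NP) children form a separate weekly group. PDFF is the subject of Aim 2 and part of the primary hypothesis.

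**The concern.** A prevalence above a threshold in a cross-sectional population sample says nothing about how far treatment moves a mean over 16 weeks, or about the spread around that mean. Cohen's f needs both. The 0.92 therefore rests on an effect size whose origin cannot be seen, and that effect size turns out to be large.

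The three power figures differ sharply: 0.17 for CIMT, 0.96 for DEXA and 0.92 for PDFF. A reader would take PDFF as one of the well-powered outcomes and could treat a null PDFF result as an informative negative. If 0.92 holds only for a very large difference, and only with 20 children in every group, that reading is unsafe.

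**Working it through.** **Inputs.** From the Power text: three groups of 20, alpha 0.05, effect size 0.49, stated power 0.92. From Appendix II Table 1, baseline PDFF in percent, mean (SD): combined 6.58 (8.54), AP weekly 6.52 (8.21), AP monthly (UC) 12.01 (7.82), NP weekly 4.72 (8.61). The Table 1 values are observed results, not planning inputs. The baseline-to-week-16 correlation r is not given anywhere and is varied below.

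**1. Reproduce the stated power.** Read 0.49 as Cohen's f and use the noncentral F with noncentrality λ = N f² = 60 × 0.49² = 14.41.
- On 2 and 57 df, power is 0.922. With one covariate (2 and 56 df) it is 0.921.
- The same method gives 0.174 for CIMT (f = 0.16, stated 0.17) and 0.956 for DEXA (f = 0.53, stated 0.96).
- Other readings of 0.49 fail. As a two-group standardised difference it gives 0.34 two-sided; as the range of three means in SD units, 0.25–0.33; as f², 0.999.

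So the index is Cohen's f and the arithmetic is sound.

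**2. Convert f to a difference.** f is the SD of the group means divided by the within-group SD. Let D be the range of the three means in SD units.
- One group differs from the other two: f = D√2/3, so D = 3 × 0.49/√2 = 1.04.
- Equally spaced means: f = D/√6, so D = 0.49 × √6 = 1.20.

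**3. Put it in PDFF points.** Under the planned ANCOVA the residual SD is 8.54 × √(1 − r²).

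| Assumed r | Residual SD | Difference needed (points) | As % of combined mean 6.58 |
|---|---|---|---|
| 0 (unadjusted) | 8.54 | 8.9–10.3 | 135–156 |
| 0.5 | 7.40 | 7.7–8.9 | 117–135 |
| 0.7 | 6.10 | 6.3–7.3 | 96–111 |
| 0.8 | 5.12 | 5.3–6.2 | 81–93 |
| 0.9 | 3.72 | 3.9–4.5 | 59–68 |

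Against the UC mean of 12.01, the unadjusted requirement is 74–85%.

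**4. Check the group sizes.** Forty AP children split 2:1 give about 27 and 13, with 20 NP children. This assumes that the planned total of 60 is kept.

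The achieved sizes have to be inferred:
- Table 1 prints n = 17 for UC, but 19 + 17 + 21 = 57, not the printed 47. With UC = 7 the weighted mean weight is (19 × 77.08 + 7 × 72.37 + 21 × 85.76)/47 = 80.26, as printed. With UC = 17 it is 78.87.
- In Table 2, the UC time effects follow η² = t²/(t² + n − 1), where t² = n × (mean change/SD)². For triglycerides (33.00, SD 30.11), n = 6 gives the printed 0.59 and n = 17 gives 0.56.
- F[2,34] with one covariate means N = 34 + 3 + 1 = 38. The laboratory means fit fifteenths in the AP weekly column (160.27 = 160 + 4/15) and seventeenths in the NP column (108.53 = 108 + 9/17). That gives 15/6/17.

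Keep the same standardised differences, with UC at one extreme as the primary hypothesis expects. Then λ = Σ nᵢ(μᵢ − μ̄)², where μ̄ is the weighted mean. If UC alone differs, λ = 1.0394² × n_UC × (N − n_UC)/N.

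| AP weekly/UC/NP | UC alone differs | Equally spaced, UC at one end |
|---|---|---|
| 20/20/20 | λ = 14.41, power 0.92 | λ = 14.41, power 0.92 |
| 27/13/20 | λ = 11.00, power 0.83 | λ = 11.59–13.23, power 0.85–0.90 |
| 15/6/17 | λ = 5.46, power 0.50 | λ = 6.80–7.14, power 0.60–0.62 |

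The pattern matters. If UC were in the middle or level with one active group, the same formula gives 0.92–0.95 at 27/13/20 and 0.77–0.84 at 15/6/17.

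**The case against.** The strongest reply is that this is a pilot. The Power text states a feasibility interest and says that limited prior research complicated the calculations. The study cited for the prevalence is not available here and may hold the inputs used. One route comes close: under normality, 33.6% against 5% above the cut-off is a shift of 1.645 − 0.423 = 1.22 SD, and for equally spaced groups f = 1.22/√6 = 0.499. That is near 0.49 but not equal to it. The documents do not describe this route, and it would be a contrast between populations rather than an effect of 16 weeks of treatment. What stands is that the derivation is not shown. It cannot be said that no derivation exists.

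The benchmark can also be challenged. The SD of 8.54 is an observed value that exceeds its mean, so the data are right-skewed, and it was not available as a planning figure. It serves as a plausibility check only.

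A reader might infer that the assumed effect is impossible because it exceeds all the liver fat present. The documents do not support that. The required difference equals 6.58 only at r of about 0.67 (one group against two) or 0.77 (equal spacing), and r is unknown. At r = 0.9 the difference is well below the mean. UC starts at 12.01, and a between-group contrast also depends on what UC does, which could include a rise.

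The missing detail is nevertheless more than a matter of reporting. Even with f = 0.49 granted, 0.92 also needs 20 children per group, and neither the 2:1 allocation nor the achieved groups provide that.

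**Conclusion.** The concern holds in a limited form. The 0.92 is not an arithmetic error, although a reader might take it for one. It is the right power for Cohen's f = 0.49 with three groups of 20. It is unsupported as the power of this trial for PDFF, for two reasons.

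First, the basis shown contains no treatment difference, SD or change, and the f implies a large effect: about 60% to over 150% of the combined baseline mean as the assumed correlation runs from 0.9 to 0. This rests on the observed, skewed baseline SD and an unknown correlation.

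Second, the group sizes do not apply. With the same standardised effect and UC at one extreme, power is about 0.83–0.90 under 2:1 allocation and 0.50–0.62 at 15/6/17. The latter sizes are inferred. Table 2 has no PDFF row and PDFF group sizes are not printed, so 0.50–0.62 should not be quoted as the actual PDFF power.

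**What to change.** Do not present 0.92 as the PDFF power. In the Power section, name the effect-size index. Restate PDFF power from a point difference that the investigators are prepared to defend, a stated SD, and a range of baseline correlations, using the 2:1 or actual group sizes. Say which pattern of group means is assumed, and print the number of children with PDFF data in each group. Report the PDFF contrasts as baseline-adjusted estimates with 95% CIs, so that a null result is not read as an adequately powered negative.

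The cost is redrafting and a less favourable stated power. No extra patients are needed.

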Understanding of Materials Scale: In order to determine the understanding of the scales and program presented, the therapist/research staff will complete an Understanding of Materials Scale after each session with both parent and child participants. This will allow the therapist and PI to periodically evaluate the general level of understanding and determine if changes to the protocol are needed.

Homework Quality Scale: Completion of homework assignments is a major component in the psychotherapy throughout this program, with the ability to impact the successful outcome of the treatment. The Homework Quality Scale will be completed by the therapist/PI after each session and will be used to assess the quality of homework in relation to the outcome of the therapy at the end of the study.

Working Alliance Inventory: The Working Alliance inventory measures the quality of the therapeutic relationship between the therapist and the patient (or youth and parent in this case). For the present study, both parent and child will be asked to anonymously fill out the "Client" version of the inventory and mail back in a self-addressed, stamped envelope provided to them at the 8 and 16 week sessions. The therapist will also fill out the Therapist version of the WAI at the same time points.

Modified TLP Therapist Fidelity Rating Checklist: This checklist includes items to assess therapist fidelity to the manualized therapy, and also includes therapist competency measures. This checklist has been used to monitor therapy fidelity in federally funded studies of both TLP and FBT behavioral weight loss programming.

DATA MANAGEMENT, SAFETY & ADVERSE EVENT REPORTING

Power: Our interest in conducting this study was to evaluate feasibility of delivering the weight loss intervention in antipsychotic (AP) treated versus nonpsychiatric (NP) overweight or obese youth, and to assess the effect of weight loss on metabolic measures of interest – CIMT/DEXA/PDDF in the AP-treated and NP active intervention groups as well as in a usual care (UC) reference group of obese youths. Comparisons of interest were between each of the two active treatment groups and UC, as well as between the two active intervention groups themselves (AP-treated vs. NP). Limited prior research in this area complicated power calculations for this pilot study.

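### The DEXA power of 0.96 is an omnibus three-group figure; the plan's named comparisons are pairwise, and the one printed difference (AP vs NP, 2 kg) has power of about 0.54

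*Combined protocol and SAP*

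**What the plan says.** The DEXA paragraph of the Power section (Appendix I) starts from "previously noted weight loss of up to 8-10% in other studies of behavioral weight loss interventions". It puts expected baseline fat at "14-15 kg of body fat, or roughly 30-40% body fat" and continues: "Anticipating up to a 5% loss from baseline fat measured by DEXA, less than the 8-10% observed in other studies". It attributes the smaller loss to mental illness and antipsychotic treatment. The only difference it prints is between the two active groups: "we estimated a difference between active treatment groups (AP-treated vs. NP) of 2 +/-3 kg loss from a baseline of 15 kg total fat". The result follows at once: "Power to detect differences in DEXA Total Fat between the 3 treatment groups", with 20 per group, alpha 0.05 and "an effect size of 0.53 was calculated to be 0.96". The type of effect size is not named and no UC loss is given.

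The opening of the Power section states what the trial compares: "Comparisons of interest were between each of the two active treatment groups and UC, as well as between the two active intervention groups themselves". The Analytic approach paragraph repeats these comparisons and makes them contrasts in an ANCOVA of the 16-week value on baseline and a three-level group factor. Specific Aims says that AP-treated children are randomised 2:1 to the weekly programme or usual care.

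**The concern.** An omnibus test asks whether any of the three groups differ. The plan asks three narrower questions: AP vs UC, NP vs UC and AP vs NP. Omnibus power can be high because one pair is far apart while the other two pairs are poorly powered. Because 0.96 comes directly after an AP vs NP difference, a reader may attach it to that comparison, or to AP vs UC, the only randomised one.

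DEXA adiposity is Aim 1, and 0.96 is the highest of the three powers printed. A null AP vs UC or AP vs NP result could then be taken as well-powered evidence of no effect. A reader also cannot check 0.53, because the assumptions behind it are incomplete.

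**Working it through.** **Inputs.** From the Power section: 3 groups of 20, alpha 0.05, effect sizes 0.16, 0.49 and 0.53 with stated powers 0.17, 0.92 and 0.96; AP vs NP 2 +/-3 kg; baseline fat 14-15 kg; losses of 5% and 8-10%. Assumptions: 3 kg is an SD of change (the paragraph refers to known SDs of mean change, but prints only +/-), and pairwise tests are two-sided.

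**1. The plan's own figures.** Read the effect size as Cohen's f and use the noncentral F distribution with 2 and 57 df and λ = 60f².

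| Outcome | f | λ | Power | Stated |
|---|---|---|---|---|
| CIMT | 0.16 | 1.54 | 0.174 | 0.17 |
| Hepatic fat | 0.49 | 14.41 | 0.922 | 0.92 |
| DEXA | 0.53 | 16.85 | 0.956 | 0.96 |

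All three reproduce. Read instead as a pairwise standardised difference, 0.53 gives only 0.37 at 20 v 20, so 0.96 is an omnibus power.

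**2. The printed difference, AP vs NP.** d = 2/3 = 0.667; noncentrality = 0.667/√(1/20 + 1/20) = 2.11; 38 df; power 0.54. If 3 kg were instead the SD of the 16-week value, ANCOVA would reduce it to 3√(1 − r²). For assumed baseline correlations r of 0.3, 0.5 and 0.7, power is 0.58, 0.66 and 0.82 (37 df).

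**3. The closest pair at f = 0.53.** Put the means at 0, a and a+b in SD units. Then f² = [a² + b² + (a+b)²]/9. For fixed f the smaller gap is largest when a = b, where it equals f√1.5 = 0.53 × 1.225 = 0.649 SD. Power at 20 v 20 is 0.516, or 0.523 with the pooled 57 df. This bound needs no value for the SD, but it does need 0.53 to be on the scale of the analysis. If 0.53 leaves out the gain from baseline adjustment, the bound becomes 0.55, 0.64 or 0.80 for r = 0.3, 0.5 or 0.7.

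**4. Can 0.53 be derived?** f needs three means and an SD, and no UC mean is printed. Assume no loss in UC, 5% in AP, 8-10% in NP, and SD 3 kg.

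- Percentages of 15 kg fat: AP 0.75 kg, NP 1.2-1.5 kg; f = 0.165-0.204; omnibus power 0.18-0.26.
- Percentages of body weight: 14/0.40 = 35 kg to 15/0.30 = 50 kg; AP 1.75-2.5 kg, NP 2.8-5.0 kg; f = 0.385-0.680; omnibus power 0.74-0.998.
- UC/AP/NP losses of 0/1.9/3.9 kg: f = 0.531; omnibus power 0.957.

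The last pattern keeps the AP vs NP gap at 2 kg and matches 0.53, but it is not in the text.

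**5. Pairwise power under 0/1.9/3.9 kg, SD 3 kg (illustration).** The 20 v 10 column is one allocation consistent with 2:1.

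| Comparison | d | 20 v 20 | 20 v 10 |
|---|---|---|---|
| AP vs UC | 0.633 | 0.50 | 0.35 |
| NP vs UC | 1.300 | 0.98 | 0.90 |
| AP vs NP | 0.667 | 0.54 | not affected |

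**The case against.** The strongest reply is that the text says the power is for differences among the three treatment groups, in the same form as the CIMT and hepatic paragraphs, and the figure is right for that. This stands. A reader might infer from the adjacent sentences that the plan claims 0.96 for the 2 kg difference, or that 0.96 is miscalculated. The documents support neither. What remains is that the plan gives no power for the comparisons it names.

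A second tempting inference is that 5% of 15 kg, or 0.75 kg, contradicts the 2 kg. It does not. The first is an anticipated loss and the second a difference between groups, so they need not be equal. The narrower point survives: the 5% is stated on fat, the 8-10% on weight, and the UC loss is missing.

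Third, ANCOVA may raise power. That is true if 3 kg is an SD of 16-week values. The reference to SDs of change makes this less likely, and even r = 0.7 gives 0.82 for AP vs NP.

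Fourth, the closest-pair bound is a general property of three-group omnibus tests, not an error peculiar to DEXA. Agreed; it shows why an omnibus figure cannot stand in for pairwise power.

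Finally, this is a pilot with a stated feasibility interest, and the plan admits that limited prior research complicated the power calculations. That limits the consequence, but not the need for the printed power to describe the plan's own comparisons.

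**Conclusion.** The point holds as one about what the power statement covers and whether its inputs can be traced. The 0.96 is correct for the omnibus test only. AP vs NP at 2 kg has power of about 0.54 (3 kg as the SD of change, 20 v 20, two-sided 0.05). With 0.53 on the analysis scale, at least one named pair has power of at most about 0.52; this is not an unconditional ceiling, because an unadjusted 0.53 would raise it.

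The 0.53 cannot be derived from the text. Depending on whether the percentages are of fat or of body weight, omnibus power runs from 0.18 to 0.998 under the assumptions shown.

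A reader might go further and say that 0.96 is carried mainly by the non-randomised NP vs UC contrast. That is so under 0/1.9/3.9 kg, but the UC mean is unstated, so the documents do not establish it. Nor do they support a demand for a larger trial, since the study is presented as a pilot.

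**What to change.** In the DEXA paragraph of the Power section:

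1. Label 0.96 as *omnibus 3-group test only*.
2. State the assumed UC, AP and NP losses, the SD and what it is an SD of, and whether the 5% and 8-10% are of fat or of body weight. If these values do not give f = 0.53, replace 0.53 and 0.96 with what they do give.
3. Add: *For AP vs NP, a 2 kg difference (SD 3 kg, 20 v 20) has power of about 0.54.*
4. Give AP vs UC and NP vs UC power under the same means at the group sizes actually planned, and reconcile 20 per group with the 2:1 randomisation in Specific Aims. The illustrative values in the working should not be copied in unless those means and sizes were the ones intended.

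The cost is a few sentences and a less favourable stated power for some of the named comparisons. Sample size and the ANCOVA stay as they are.
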